4.11.2.3 FACIT Item GP-5

FACIT Item GP-5 assesses the level to which each participant is bothered by side effects of treatment. It is a single score on a 5-point scale ranging from “not at all [bothered]” (0) to “Very much [bothered]” (4).

Results from the FACIT Item GP-5 will be summarized descriptively by visit, including a shift table from baseline to worst on treatment. Worst on treatment is defined as the highest numerical state while on treatment (e.g., 4 is worse than 3).

Plots of mean change from baseline value over time will also be presented with indicators for the number of patients at each visit.

4.11.3 Health Economics

Medical resource utilization and health economics parameters are not evaluated in this study.

4.12 Determination of Sample Size

Approximately 100 participants will be enrolled and dosed in the study with approximately 50 participants in each line of therapy (1L or 2L). Assuming at least 80% of participants have measurable disease, approximately 40 of the planned 50 participants will have measurable disease per line of therapy. This sample size will allow an estimate of ORR with the half width of the 95% CI of no larger than approximately 16%.

4.13 Changes in the Conduct of the Study or Planned Analysis

This SAP is based on the Study EQ132-201 protocol Version 3.0, Amendment 3, dated February 27, 2023. This amendment is considered substantial, based on the criteria set forth in Article 10(a) of Directive 2001/20/EC of the European Parliament and the Council of the European Union. However, it does not significantly impact analysis endpoints or methodology.

In addition, no changes to the statistical methods detailed in the study protocol have been implemented in this document.

6 APPENDIX

6.1 Schedule of Assessments

| Procedure | Screening | Treatment Phase | | | | | | Post-Treatment Follow-up Phase | |
|--|-------------|-----------------|----------|----------|----------|-------------------|--|-----------------------------------|--------------------------|
| | | Cycle 1 | | Cycle 2 | Cycle 3 | Subsequent Cycles | EOT/ED (as applicable) | Safety Follow-up | Survival Follow-up Phase |
| Study Day(s) | D-42 to D-1 | D1 | D15 | D1 | D1 | D1 | Within 15 days after last dose of lerociclib | Last dose of lerociclib + 30 days | Every 12 weeks |
| Visit Window (days) | - | - | ± 2 days | ± 2 days | ± 2 days | ± 2 days | - | + 5 days | ± 7 days |
| Informed consent | X | | | | | | | | |
| IRT participant number assignment (after ICF signature) | X | | | | | | | | |
| Participant ID card distribution | | X | | | | | | | |
| Inclusion/exclusion criteria | X | X | | | | | | | |
| Demography | X | | | | | | | | |
| Medical history and current medical conditions (including details on cancer diagnosis, extent of cancer, and prior anticancer therapy) | X | | | | | | | | |
| Estrogen receptor, progesterone receptor, and HER2 status | X | | | | | | | | |

Parexel International

EQRx, Inc.

Protocol Number: EQ132-201

Statistical Analysis Plan

| Procedure | Screening | Treatment Phase | | | | | | Post-Treatment Follow-up Phase | |
|--|----------------|-----------------|----------------|----------------|----------------|-------------------|--|-----------------------------------|--------------------------|
| | | Cycle 1 | | Cycle 2 | Cycle 3 | Subsequent Cycles | EOT/ED (as applicable) | Safety Follow-up | Survival Follow-up Phase |
| Study Day(s) | D-42 to D-1 | D1 | D15 | D1 | D1 | D1 | Within 15 days after last dose of lerociclib | Last dose of lerociclib + 30 days | Every 12 weeks |
| Visit Window (days) | - | - | ± 2 days | ± 2 days | ± 2 days | ± 2 days | - | + 5 days | ± 7 days |
| Current line of endocrine therapy for mBC | X | | | | | | | | |
| Prior medications review (including prior antineoplastic therapy) | X | | | | | | | | |
| Concomitant medications review | | X (continuous) | | | | | | X | |
| Physical examination | X | X ^a | | X ^a | X ^a | X ^a | X | | |
| Height | X | | | | | | | | |
| Body weight | X | X | | X | X | X | X | | |
| ECOG PS | X | X | | X | X | X | X | | |
| Clinical laboratory tests (hematology, clinical chemistry, coagulation, fasting lipid panel, and urinalysis) | X ^b | X ^c | X ^c | X ^c | X ^c | X ^c | X | | |
| Pregnancy test ^d | X ^b | X | | | | | | | |

Parexel International

EQRx, Inc.

Protocol Number: EQ132-201

Statistical Analysis Plan

| Procedure | Screening | Treatment Phase | | | | | | Post-Treatment Follow-up Phase | |
|--|----------------|--|----------|----------|----------|----------------------------|--|-----------------------------------|--------------------------|
| | | Cycle 1 | | Cycle 2 | Cycle 3 | Subsequent Cycles | EOT/ED (as applicable) | Safety Follow-up | Survival Follow-up Phase |
| Study Day(s) | D-42 to D-1 | D1 | D15 | D1 | D1 | D1 | Within 15 days after last dose of lerociclib | Last dose of lerociclib + 30 days | Every 12 weeks |
| Visit Window (days) | - | - | ± 2 days | ± 2 days | ± 2 days | ± 2 days | - | + 5 days | ± 7 days |
| FSH measurement (female participants only) | X | | | | | | | | |
| 12-lead ECG ^e | X ^b | X | X | X | X | X (at Cycles 4 and 5 only) | X | | |
| ECHO or MUGA with EF | | As clinically indicated by Investigator | | | | | | | |
| Vital signs | X | X | X | X | X | X | X | | |
| PK sampling ^f | | X | X | X | X | X (at Cycles 4 and 5 only) | | | |
| Tumor evaluation (per RECIST v1.1) | X | Every 8 weeks (± 7 days) during the first 12 months and every 12 weeks (± 7 days) thereafter until disease progression, death, withdrawal of consent, loss to follow-up, or participant/legally acceptable representative decision, and at EOT/ED (as applicable). If PR/CR is reported, confirmation of response is required; confirmatory assessment should be performed ≥ 4 weeks after response is first documented. ¹ | | | | | | | |

Parexel International

EQRx, Inc.

Protocol Number: EQ132-201

Statistical Analysis Plan

| Procedure | Screening | Treatment Phase | | | | | | Post-Treatment Follow-up Phase | |
|--|--|--|----------|----------|----------|-------------------|--|-----------------------------------|--------------------------|
| | | Cycle 1 | | Cycle 2 | Cycle 3 | Subsequent Cycles | EOT/ED (as applicable) | Safety Follow-up | Survival Follow-up Phase |
| Study Day(s) | D-42 to D-1 | D1 | D15 | D1 | D1 | D1 | Within 15 days after last dose of lerociclib | Last dose of lerociclib + 30 days | Every 12 weeks |
| Visit Window (days) | - | - | ± 2 days | ± 2 days | ± 2 days | ± 2 days | - | + 5 days | ± 7 days |
| Whole-body bone scan ^g | X | Every 8 weeks (± 7 days) for the first 12 months, then: -If initial bone scan is positive for bony lesion, every 12 weeks thereafter, OR -If initial bone scan is negative for bony lesion, bone scan can be done annually or per Investigator standard of care. | | | | | | | |
| Lerociclib administration | | Twice daily continuously in 28-day cycles ^h | | | | | | | |
| Letrozole administration ⁱ | | Once daily continuously in 28-day cycles | | | | | | | |
| Fulvestrant administration ⁱ | | X | X | X | X | X | | | |
| Goserelin administration ^j | X | X | | X | X | X | | | |
| AE/SAE review | X (continuous from Screening through 30 days after last study intervention dose) | | | | | | | | |
| PROs: EORTC-QLQ-C30 (version 3), EQ-5D-5L, FACIT Item GP 5 | X ^b | On Day 1 of each cycle (before any other study procedures) until disease progression, death, withdrawal of consent, loss to follow-up, or participant/legally acceptable representative decision, and at EOT. | | | | | | | |
| PRO: EORTC-QLQ-BR23 | X ^b | On Day 1 of every other cycle (before any other study procedures) until disease progression, death, withdrawal of consent, loss to follow-up, or participant/legally acceptable representative decision, and at EOT. | | | | | | | |

Parexel International

EQRx, Inc.

Protocol Number: EQ132-201

Statistical Analysis Plan

| Procedure | Screening | Treatment Phase | | | | | | Post-Treatment Follow-up Phase | |
|--|-------------|-----------------|----------|----------|----------|-------------------|--|-----------------------------------|--------------------------|
| | | Cycle 1 | | Cycle 2 | Cycle 3 | Subsequent Cycles | EOT/ED (as applicable) | Safety Follow-up | Survival Follow-up Phase |
| Study Day(s) | D-42 to D-1 | D1 | D15 | D1 | D1 | D1 | Within 15 days after last dose of lerociclib | Last dose of lerociclib + 30 days | Every 12 weeks |
| Visit Window (days) | - | - | ± 2 days | ± 2 days | ± 2 days | ± 2 days | - | + 5 days | ± 7 days |
| Collection of information on new anticancer therapies, as applicable | | | | | | | X | X | X |
| Survival follow-up | | | | | | | | | X ^k |

- A physical examination is to be performed on Day 1 of every cycle. According to Investigator's judgment, this can be an abbreviated physical examination.
- To be performed between Day -7 and Day -1.
- Results of clinical laboratory tests (hematology, clinical chemistry, coagulation, fasting lipid panel, and urinalysis) must be available prior to the administration of lerociclib on Day 1 of each cycle and on Day 15 of Cycle 1. Clinical laboratory tests may be obtained up to 24 hours prior to the scheduled visit.
- For female study participants who are WOCBP (as defined in Protocol Appendix 4) only: Serum β -hCG pregnancy test will be performed at Screening. Serum or urine β -hCG pregnancy test will be performed at Cycle 1 Day 1 before the administration of the first dose of lerociclib. Beyond this timepoint, pregnancy test(s) may be performed at the discretion of the Investigator.
- Participants will receive 12-lead ECGs (triplicate) at pre-dose and at 2 hours and 6 hours (± 10 minutes) after their lerociclib dose on Day 1 and Day 15 of Cycle 1, and then on Day 1 of Cycles 2, 3, 4, and 5. Triplicate 12-lead ECGs shall be obtained within a 5-minute period and shall be performed prior to blood draws whenever applicable. The same make and model of ECG machine should be used within each participant. In addition to triplicate 12-lead ECGs, a single 12-lead ECG will be collected (prior to blood draws) at Screening and at the EOT/EOD Visit. Other than at the EOT/EOD Visit, ECGs will not be conducted beyond Cycle 5 unless clinically indicated.
- Pre-dose and post-dose blood samples for lerociclib concentration measurement are to be collected prior to and following the dose of lerociclib on Day 1 and Day 15 of Cycle 1, and on Day 1 of Cycles 2, 3, 4, and 5. The post-dose blood sample can be collected between 2 hours and 6 hours (± 10 minutes) after the administration of lerociclib. It is important to record the actual time of collection. If the participant is due for a 2- or 6-hour 12-lead ECG assessment, the PK sample may be drawn at the same timepoint but should be obtained after the ECG.
- Radionuclide bone scans shall be performed at Screening for all participants every 8 weeks (± 7 days) for the first 12 months and every 12 weeks thereafter if initial bone scan is positive for bony lesion. If initial bone scan is negative for bony lesion, bone scan should be done annually or as clinically indicated per Investigator standard of care.

Parexel International

EQRx, Inc.

Protocol Number: EQ132-201

Statistical Analysis Plan

All participants with a CR must have a radionuclide bone scan as part of confirmation of the CR. Additional bone scans may be obtained at the discretion of the Investigator, if clinically indicated. Participants with bone-only disease may be followed only with bone scans at the discretion of the Investigator. If CT or bone scan have been done for regular clinical care within 28 days before receiving the first dose of lerociclib, these may be used as baseline scans.

- h. Subsequent cycles may be postponed up to 14 days due to lerociclib interruption.
- i. Participants in the 1L and 2L populations will receive the Investigator's choice of letrozole 2.5 mg daily or fulvestrant 500 mg (dosed according to schedule specified in the protocol).
- j. All premenopausal or perimenopausal female participants, and all male participants, must be receiving goserelin for at least 28 days prior to entering the study and will remain on goserelin throughout the study, in accordance with the prescribing information and according to the study site's standard practice. For all study participants (female or male) receiving goserelin, their treatment with goserelin must start at least 28 days before their first dose of lerociclib.
- k. After the Safety Follow-up Visit, survival follow-up should be attempted every 12 weeks for each participant in the long-term Survival Follow-up Phase. Follow-up can be performed via telephone, clinic visits, or by receiving information from a family member or another provider who is administering care. Any anticancer therapies used will be collected where possible.
- l. CT or MRI scans obtained prior to informed consent will not need to be repeated if performed within 28 days prior to dosing with lerociclib.

Abbreviations: AE = adverse event; β -hCG = human beta chorionic gonadotrophin; CR = complete response; CT = computed tomography; ECG = electrocardiogram; ECHO = echocardiogram; ECOG PS = Eastern Cooperation Oncology Group performance status; ED = early discontinuation; EF = ejection fraction; EQ-5D-5L = EuroQoL 5-dimension 5-level; EORTC-QLQ = European Organisation for the Research and Treatment of Cancer Quality of Life Questionnaire; EOT = end of treatment; FACIT = Functional Assessment of Chronic Illness Therapy; FSH = follicle-stimulating hormone; HER2 = human epidermal growth factor receptor 2; ICF = informed consent form; ID = identification; IRT = interactive response technology; mBC = metastatic breast cancer; MRI = magnetic resonance imaging; MUGA = multigated acquisition; PK = pharmacokinetic(s); PR = partial response; PRO = patient-reported outcome; RECIST v1.1 = Response Evaluation Criteria in Solid Tumors, version 1.1; SAE = serious adverse event; WOCBP = women of childbearing potential.

6.2 Imputation Rules for Partial or Missing Dates

Imputation of partial dates will be made for AE onset and stop dates, start and end dates of concomitant medication, start date of subsequent therapy, and death date. If dates are completely missing, no imputation will be made. For any partial date with missing year, no imputation will be made.

The general rule for imputation is:

- If only day is missing, then the 15th of the month will be used.
- If only year is present, then June 30th will be used.

If such imputation date for diagnosis is on or after date of first dose, the date of first dose – 1 will be used.

If such imputed date for subsequent therapies is before date of last dose, the date of last dose + 1 will be used.

If the imputed date is for an AE start date and is in the same year and month as the first dose date but before the first dose date, the first dose date will be used, or if the imputed AE start date is after the AE end date, the AE end date will be used.

If the imputed date is for an AE start date and is in the same year and month as last dose date + 30 days but after the last dose date + 30 days, the last dose date + 30 days will be used.

If the imputed date is for an AE end date and is after the death date, the death date will be used, or if the imputed AE end date is before the AE start date, the AE start date will be used.

For the missing death dates, if death year and month are available but day is missing:

- If mmyyyy for last contact date still alive = mmyyyy for death date, set death date to the day after the last contact date.
- If mmyyyy for last contact date still alive < mmyyyy for death date, set death date to the first day of the death month.

If both month and day are missing for death date or a death date is entirely missing, do not impute and censor the participant survival time.

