- j. All premenopausal or perimenopausal female participants, and all male participants, must be receiving goserelin for at least 28 days prior to entering the study and will remain on goserelin throughout the study, in accordance with the prescribing information and according to the study site's standard practice. The goserelin dosing schedule is decoupled from the rest of the study visit schedule, with each participant's "goserelin CID1" determined as the date of their most recent goserelin dose before entering the study + 28 days. Goserelin dosing will continue on a q28d basis throughout the participant's time on study. All of the participant's non-goserelin-dosing study activities are to occur as shown in the Schedule of Activities.
- k. After the Safety Follow-up Visit, survival follow-up should be attempted every 12 weeks for each participant in the long-term Survival Follow-up Phase. Follow-up can be performed via telephone, clinic visits, or by receiving information from a family member or another provider who is administering care. Any anticancer therapies used will be recorded where possible, as well as any changes to participant pregnancy status (as applicable).
- l. CT or MRI scans obtained prior to informed consent will not need to be repeated if performed within 28 days prior to dosing with lerociclib.

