4.9.1.3 Treatment-emergent Adverse Events (TEAEs)

Treatment-emergent adverse events (TEAEs) will be tabulated and are defined as those adverse events that either start or worsen in severity on or after the date/time of first dose of study treatment through 30 days after end of treatment or the day before initiation of a new antineoplastic treatment, whichever occurs first. Where dates are missing or partially missing, AEs will be assumed to be treatment-emergent, unless there is clear evidence (through comparison of partial dates) to suggest that the adverse event started prior to the first dose of study treatment or after the Post-Treatment Follow-up visit. Partial dates will be imputed per rules outlined in [Appendix 6.2](#).

An overall summary table will be created to present high level TEAE and treatment-related adverse event (TRAE) information. The following will be summarized (presenting the number of participants and number of events) by line of therapy, system organ class (SOC), and preferred term (PT):

- TEAEs
- TRAEs
- Serious TEAEs
- Serious TRAEs
- For each study treatment
 - TEAEs Leading to Drug Discontinuation
 - TEAEs Leading to Drug Reduction
 - TEAEs Leading to Drug Interruption
 - TEAEs Leading to Drug Reduction or Interruption

Additionally, the following summaries presenting the number of participants and number of events will also be created:

- TEAEs by line of therapy and PT
- TEAEs in >10% of participants by line of therapy and PT
- TRAEs by line of therapy and PT
- TEAEs by line of therapy, maximum severity grade, SOC, and PT (number of participants only)

Adverse event summaries will be ordered alphabetically for SOC, and decreasing frequency of PT within SOC for the total column (including both lines of therapy).

For each participant and each adverse event, the worst severity recorded will be attributed and used in the by-severity summaries. Similarly, the worst causality (most related to Lerociclib) will be attributed and used in the by-causality summaries. If severity or causality is missing, a conservative approach for AE assessment (implementing the worst case) will be followed.

Adverse events of special interest (AESIs) TEAEs and TRAEs will also be summarized by line of therapy, maximum severity grade, SOC, and PT for the following terms:

| AESI | Definition |
|---------------------------|-----------------------|
| Febrile neutropenia | MedDRA code #10016288 |
| Pneumonitis | MedDRA code #10035742 |

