4.10.3.2 Progression-free Survival (PFS)

Progression-Free Survival (PFS) is defined as the time to PFS event from first exposure to lerociclib. PFS event is defined as PD (per RECIST v1.1 as assessed by the investigator) or death due to any cause, whichever comes first. For participants without death or disease progression, PFS will be censored at the date of the last valid RECIST assessment unless otherwise stated. PFS duration will be calculated as

$$\text{Date of observation} - \text{Date of first exposure to lerociclib} + 1$$

where date of observation is the earliest of death, progression, or censoring.

PFS events and censoring rules, such as initiation of disallowed anticancer therapy, are defined below in Table 2.

All valid RECIST assessments after start of treatment will be used in the PFS analysis regardless of whether they were collected as part of scheduled or unscheduled visits. RECIST assessments based on scans performed after the end of lerociclib therapy will be used in the analysis of PFS if prior censoring events have not been observed.

Table 2 Censoring Rules for Progression-Free Survival

| Situation | Outcome | Date of Event/ Censoring |
|--|---------|---|
| PD or death, whichever occurred first, before exposure to subsequent antineoplastic therapy, withdrawal of consent, loss to follow up, data cutoff, or end of study. | Event | Earliest date of documented progression or death |
| No baseline disease assessment | Censor | Date of first exposure |
| No valid post-baseline tumor assessment | Censor | Date of first exposure |
| PD or death immediately after missing ≥ 2 consecutive scheduled tumor assessment | Censor | Date of last valid tumor assessment prior to the missing tumor assessments |
| No PD or death on or before 
 Database cut End of study Start of new antineoplastic therapy | Censor | Date of last tumor assessment on or prior to earliest censoring event listed in first column of this row. |

Descriptive summaries of time to event data will include median, twenty-fifth and seventy-fifth percentiles, and associated 2-sided 95% CIs based on Kaplan-Meier methods. Survival estimates along with corresponding 95% CIs using the log-log transformation will be provided at certain intervals as data allows.

A Kaplan-Meier plot will be presented and will include the number of participants at risk over time by line of therapy. No formal statistical hypothesis will be tested.

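### A partly recorded start date for the next cancer therapy can, once imputed, end the TEAE window on the last-dose day and censor a progression found after the last dose

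*SAP*

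**What the plan says.** SAP 6.2 imputes partial start dates of subsequent therapy in three steps.

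- Day missing: "If only day is missing, then the 15th of the month will be used".
- Day and month missing: "If only year is present, then June 30th will be used".
- Then a floor: "If such imputed date for subsequent therapies is before date of last dose, the date of last dose + 1 will be used".

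Nothing is imputed when the year is unknown: "For any partial date with missing year, no imputation will be made".

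Two analyses use the resulting date. SAP 4.9.1.3 counts an AE as treatment-emergent from first dose "through 30 days after end of treatment or the day before initiation of a new antineoplastic treatment, whichever occurs first". SAP 4.10.3.2, Table 2, counts as a PFS event only "PD or death, whichever occurred first, before exposure to subsequent antineoplastic therapy"; otherwise the participant is censored at the last tumor assessment on or before the new therapy. SAP 4.10.3.4 applies the same censoring to DOR.

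On data collection, the Schedule of Activities (Protocol 1.3) asks about new anticancer therapy at EOT/ED, at Safety Follow-up and during Survival Follow-up. Footnote k allows survival follow-up by telephone, or through family or another provider, and says: "Any anticancer therapies used will be recorded where possible".

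**The concern.** The last-dose-plus-one date is the earliest start possible after treatment ends. When it is used, the TEAE window keeps no day after the last dose. Yet the protocol collects AEs through 30 days after the last study intervention dose and schedules a safety visit for that time. The AE listings in SAP 4.9.1.3 cover TEAEs and serious TEAEs only, so an excluded SAE would be missing from those listings as well as from the tables.

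This goes against the SAP's handling of uncertain AE dates. Section 4.9.1.3 presumes an AE with a missing or partial date to be treatment-emergent, and 6.2 pulls same-month AE onsets back into the window. An uncertain therapy date can do the opposite, and can exclude an AE whose own date is complete.

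For PFS and DOR, progression after the last dose is foreseen. The EOT/ED tumor window in SAP 4.10.1.3 runs to last dose + 15 days, and Protocol 7.1.1 requires a scan after stopping for reasons other than progression if there was none in the prior 4 weeks. An imputed therapy start can fall before such a scan.

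**Working it through.** The plan gives no figure for this point. The check applies the date rules literally, taking end of treatment as the last dose.

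**Rules**

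- D = imputed start (the 15th or 30 June); if D < last dose, D = last dose + 1.
- TEAE window end = min(last dose + 30, D − 1).
- Progression is a PFS event only if its date is before D.

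If the reset fires, the window end is min(last dose + 30, last dose + 1 − 1) = last dose, which leaves 0 days.

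**Worked records (2023)**

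| Last dose | True start | Recorded | First imputed | Used | Post-dose window: true | Post-dose window: by rule | Without the reset |
|---|---|---|---|---|---|---|---|
| 5 Oct | 10 Nov | year only | 30 Jun | 6 Oct | 30 d | 0 d | −98 d |
| 20 Mar | 31 Mar | Mar | 15 Mar | 21 Mar | 10 d | 0 d | −6 d |
| 10 Mar | 28 Mar | Mar | 15 Mar | 15 Mar | 17 d | 4 d | 4 d |
| 20 Mar | 10 Apr | Apr | 15 Apr | 15 Apr | 20 d | 25 d | 25 d |

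In row 1, an SAE on 15 October is lost although the new therapy began on 10 November. In row 4 the window is too long. The last column shows that without the reset the window would close before the last dose in rows 1 and 2.

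**Progression**

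- By the mid-month rule: in row 3, progression on an EOT scan of 20 March precedes the true start (28 March) but follows the imputed one (15 March), so it is censored. No reset is involved, because 15 March is after the last dose.
- By the reset: last dose 10 September, therapy recorded by year only, true start 1 November. D is 30 June, reset to 11 September. Progression on 18 September, say, is censored at the last assessment on or before 11 September.
- When the reset fires, progression on or before the last dose stays an event, and progression from last dose + 2 is censored. Last dose + 1 is ambiguous, since Table 2 says before in the event row and on or prior to in the censoring row.

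**Size per participant with a partial date**

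Assumptions: last dose on each day of 2023 in turn; true gap to next therapy evenly spread over the stated range; progression evenly spread over days 0–15 after last dose and before the true start. Progression on the imputed day counts as censored.

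| Recorded | True gap (days) | Post-dose window zero or less | Window too short (mean loss) | Window too long | Such progressions censored |
|---|---|---|---|---|---|
| Year only | 7–28 | 46% | 50% (15.7 d) | 49% | 44% |
| Year only | 14–42 | 43% | 50% (23.0 d) | 29% | 42% |
| Year only | 7–60 | 42% | 48% (22.4 d) | 22% | 40% |
| Day missing | 7–28 | 9% | 51% (7.7 d) | 46% | 18% |
| Day missing | 14–42 | 1% | 43% (7.6 d) | 27% | 7% |
| Day missing | 7–60 | 4% | 30% (7.3 d) | 20% | 7% |

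The reset accounts for about 95% of the censored progressions with year-only dates, but only 3–20% when just the day is missing; the mid-month rule causes the rest. When the reset fires, the window lost is at most 14 days with only the day missing and a true start after the last dose, and at most 30 days with a year-only date.

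**The case against.** A reader might infer that the reset itself shortens the TEAE window and creates the censoring. It does not. It fires only when the imputed date is before the last dose, and it moves that date later. Deleting it would shorten the window further and censor more progressions. The fault lies in the imputation convention as a whole.

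The errors also run both ways, as the too-long column shows.

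Year-only dates may be rare for therapy begun soon after the last dose, because sites ask at EOT/ED and at Safety Follow-up, and the telephone and family route starts only afterwards. That is a fair limit on frequency, but it does not remove the problem. With true starts 31–120 days after the last dose, where the window should be the full 30 days, a year-only date still leaves zero or fewer post-dose days in about 30% of cases.

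Many progressions are the reason for stopping and fall on or before the last dose, where they are safe. A lost AE changes participant incidence only if that participant had no earlier event in the same category, although event counts and serious-event listings change regardless. Both points stand.

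Finally, the presumption in 4.9.1.3 that AEs with uncertain dates are treatment-emergent is not expressly limited to AE dates, so it could be read as covering therapy dates too. But the same paragraph sends partial dates to 6.2, which imputes the therapy date. The text does not settle the question.

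**Conclusion.** The point holds for subsequent-therapy dates that are partial with a known year, and mainly for year-only dates. For these the SAP can remove post-dose AEs and SAEs from the primary endpoint when the next therapy had not yet begun, contrary to its own approach to uncertain AE dates. It can also censor a post-dose progression for PFS and DOR, through either the mid-point convention or the reset. Complete dates, dates without a year, and progressions on or before the last dose are unaffected.

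The percentages are conditional on a partial date and on the assumed gaps. The documents give no rate of partial dates, so a reader should not infer a material bias in AE incidence, PFS or DOR for the trial as a whole. The analyses are descriptive and no test depends on this. It is a cheap improvement to the SAP, worth making because each line of therapy has only about 50 participants.

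**What to change.** In SAP 4.9.1.3 and 6.2, state that an imputed start of new therapy does not end the TEAE window. Use the full 30 days after end of treatment unless the recorded part of the date proves an earlier start. For example, with last dose on 20 March and therapy recorded as March, the latest possible start is 31 March, so the window ends on 30 March. Keep the last-dose-plus-one floor wherever an imputed date is still used.

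For PFS and DOR, keep the main rule and add a sensitivity analysis that counts progression as an event when the recorded part of the date is compatible with a therapy start after it. Making the main imputation depend on the progression date would tie it to the outcome, so this belongs in a sensitivity analysis. Report how many participants have partial therapy dates, and make the event and censoring rows of Table 2 agree for a progression dated on the day therapy starts.

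The cost is a few SAP sentences, a small programming change and one extra analysis. The downside is that a few AEs arising under the next therapy may be counted as treatment-emergent, which is the cautious direction for a safety endpoint.
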